This is a multi-institution, prospective, randomized study evaluating IVFE dose reduction on the development of PNAC as a proxy measure of PNALD in neonates requiring prolonged PN. The definition of PNAC will be that used predominantly in the literature – a direct bilirubin level of ≥ 2 mg/dL, documented on two occasions 1 week apart, in patients who have required parenteral nutrition for more than 2 weeks. **Eligible neonates will be randomized into two treatment arms: standard IVFE administration (3 g/kg/day) or IVFE reduction (IFER) (1 g/kg/day).** A total of 60 subjects (30 subjects per arm) will be included in the study. The study will evaluate

short- and long-term outcomes of this strategy. In the short-term, infants will be followed for up to 12 weeks for the development of PNAC. If a subject's PN is discontinued before 12 weeks, and if they remain in the hospital, follow-up data will be collected for an additional 7 days but not beyond a total of 84 days. Only standard-of-care data will be collected during these 7 days. No procedures will be performed for the purpose of this study during these 7 days. In the long-term, subjects' neurodevelopmental outcomes will be assessed at 12 and 24 months corrected gestational age (± 2 weeks).

Primary outcome measure:

1. The rate of rise of direct bilirubin as a function of time (mg/dL/week) between the two groups over 12 weeks or until the subject has been off of PN for >7 days, whichever comes first.

Secondary outcome measures

1. Initial 12 week period:
 - a. The incidence of PNAC (direct bilirubin ≥ 2 mg/dL) and severe PNAC (direct bilirubin ≥ 4 mg/dL in subjects on parenteral nutrition for at least 2 weeks)
 - b. The time to development of PNAC and severe PNAC
 - c. The peak total and direct bilirubin levels
 - d. The incidence of EFAD
 - e. Adequacy of growth as evaluated by z-scores for weight, height, and head circumference
 - f. Other safety measures assessed during the initial 12 week period will include adverse events (e.g., episodes of sepsis and catheter-related blood stream infections).
2. Long-term follow-up:

Neurodevelopmental assessments will include:

 - a. At 12 months corrected gestational age (± 2 weeks):
 - i. Bayley Scales for Infant and Toddler Development (BSID-III)
 - b. At 24 months corrected gestational age (± 2 weeks):
 - i. Bayley Scales for Infant and Toddler Development (BSID-III)
 - ii. MacArthur-Bates Communicative Development Inventories (CDI)

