each of these four time points is 1. The correlation of any two adjacent measures on the same individual is 0.5. This correlation drops to 0.354 between baseline and 8 weeks and to 0.25 between baseline and 12 weeks.

Using the above assumptions, a sample size of 15 subjects per group using a repeated measures ANOVA will have 85% power to detect the change in slopes as being significant at the 0.05 level, 79% power to detect a difference in means overall between groups and 88% power to detect the general change in means over time across the two groups. When the sample size is increased to 20 subjects per group, the above power numbers increase to 95%, 90% and 96%, respectively. If 30 subjects are recruited per group this design will allow for a 33% attrition rate by twelve weeks as we expect that not all patients will require PN for the full 12 weeks of the initial study period. Thus, we will recruit a minimum of 30 subjects per group to ensure adequate power to detect our primary outcome measure.

Of the secondary outcomes, sample size was also calculated for the incidence of cholestasis. Assuming an incidence of 50% in the standard group and an incidence of 10% in the minimization group, with $\alpha = 0.05$ and power of 80%, a sample size of 23 is required for each group. Regarding the other secondary outcomes, our sample size is large enough to allow for establishing trends which may then highlight avenues for future research.

Planned Statistical Analysis

All data analysis will be directed and performed by a statistician through the Center for Statistical Consultation and Research at the University of Michigan (<http://cscar.research.umich.edu/about/>). Data will be analyzed using SAS software release 9.3 for Windows (Copyright, SAS Institute Inc., SAS and all other SAS Institute Inc. product of service names are registered trademarks or trademarks of SAS Institute Inc., Cary, NC, USA). All study subjects will be included in the statistical analysis in an intent-to-treat manner.

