These measures will be compared between the two treatment groups using a linear mixed model.

3. Incidence of PNAC, severe PNAC, and EFAD

The number of occurrences of each of these outcomes will be compared using either a Poisson regression model or a negative binomial model if the variance in these counts is greater than expected for a Poisson distribution. We will also include the time on TPN as an offset, so that we can compare the rates of occurrence of each of these outcomes for the two treatment groups. These regression models will be adjusted for the covariates such as development of sepsis, average IVFE dose, and percentage of enteral feeds.

4. Adequacy of growth as evaluated by z-scores for weight, height and head circumference

The z-scores for each of these measures will be compared between the two treatment groups using a linear mixed model. For normally growing infants, we would expect that there would not be a trend in z-scores because we would expect them to maintain their curve. However, for the subjects in this study, there may be a loss in z-score over time due to inadequate growth. The slopes of the changes in these z-scores over time will be compared between the two treatment arms. A random intercept will be included for each subject to allow for individual variability in average values as well as a random slope to allow for variability in the rate of change over time across subjects. Important covariates, such as gestational age (<32 weeks gestation vs. ≥32 weeks gestation) and birth weight will also be used as covariates in this analysis.

5. Neurodevelopmental Outcomes

Bayley Scales of Infant and Toddler Development (BSID-III):⁴⁵ Raw scores are converted to composite and subscale scores using age-standardized norms. Scale composite average internal consistency reliability coefficients range from .91 to .93 with subtest reliability ranging from .86 to .91. Validity-related studies indicate relatively high correlations (.72-.79) with the Wechsler Preschool and Primary Scale of Intelligence – Third Edition (WPPSI-III)⁵³ and with the Preschool Language Scale – Fourth Edition (PLS-4)(.71-.83).⁵⁴

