outcomes: mean IVFE dose, duration of IFER and the development of essential fatty acid deficiency. Since total and direct bilirubin are expected to be highly collinear, we will use only one of these predictors and compare the models using AIC and BIC to decide which is a better predictor of the particular outcome being assessed.

A logistic regression with Generalized Estimating Equations (GEE) approach will be used to compare the binary outcomes between groups.

Intent to Treat

All statistical analyses will be performed using an intent to treat approach.

Potential Confounding Variables:

Nutritional intake: Differences in nutritional intake alter the risk of PNAC as any amount of enteral nutrition has been shown to enhance rehabilitation.⁵⁹ Infants able to tolerate even trophic amounts of enteral calories will be at decreased risk compared to those than those who are completely PN-dependent. Every attempt will be made to standardize enteral feeding advancement. This will be possible because of the relatively homogeneous nature of the subjects enrolled and their similar expected ability to tolerate enteral feeds. Statistical analyses will account for variations in enteral intake. Overfeeding may result in hepatic steatosis that can also worsen PNAC, therefore all subjects will follow a strict guideline for PN administration. Additionally, the administration of breast milk, which contains proteins necessary for optimal brain development, may be a confounding variable and will be accounted for in the final data analysis. PN duration (with or without IFER) may also affect neurodevelopmental outcomes and will be included as a covariate in the statistical analysis.

Variation in IVFE dose: The IVFE dose may vary depending on the clinical status of the subject (e.g. elevated TG, EFAD, direct bilirubin ≥ 2.5 mg/dL, nutritional and/or fluid status). Every attempt will be made to maintain dosing within the assigned treatment arm. Based on previous experience using IFER at the University of Michigan, hypertriglyceridemia and EFAD are exceedingly rare occurrences, therefore, the IVFE dose is not expected to be adjusted frequently based on these findings. Statistical analysis will account for differences in IVFE dose by using the mean IVFE dose as well as the duration of IVFE/IFER as a covariate.

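### PNAC incidence is sized as a comparison of per-infant proportions but analysed with a Poisson rate model, whose model-based standard error is too large for a yes/no outcome

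*Combined protocol and SAP*

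**What the plan says.** Sample Size Determination: "Of the secondary outcomes, sample size was also calculated for the incidence of cholestasis". The inputs are per-infant proportions, "Assuming an incidence of 50% in the standard group and an incidence of 10% in the minimization group", and the result is "with $\alpha = 0.05$ and power of 80%, a sample size of 23 is required for each group". Neither the test nor its sidedness is named. Planned enrolment is larger: "A total of 60 subjects (30 subjects per arm) will be included in the study" (Study Design).

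Secondary Outcome Measures, item 3, covers PNAC, severe PNAC and EFAD together. Its method is: "The number of occurrences of each of these outcomes will be compared using either a Poisson regression model or a negative binomial model". The negative binomial model is for variance above the Poisson value. On exposure: "We will also include the time on TPN as an offset". The models are adjusted for sepsis, average IVFE dose and enteral feeding. Item 3 does not mention a robust variance, a choice between Wald and likelihood-ratio tests, or a rule for repeat episodes.

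Study Design defines PNAC as direct bilirubin at or above 2 mg/dL on two occasions one week apart, and gives no rule for resolution or recurrence. Item 1 of the secondary outcomes analyses time to the first PNAC by Kaplan-Meier and Cox methods.

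**The concern.** The plan sizes one analysis and specifies another. A proportion of infants is a 0/1 outcome with variance p(1-p). A Poisson model assumes variance p, so its model-based standard error is too large whenever p is not small. The only fallback in the plan adds variance, and here there is too much already.

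The offset raises a second problem. Time on TPN is observed after randomisation and, as worded, is not cut off at the event. If cholestatic infants stay on TPN longer (an assumption; the documents give no figure), the arm with more PNAC gains exposure time and the rate ratio moves towards 1.

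At stake are the width of the interval for the secondary outcome that has its own sample-size calculation, and whether the 80% power statement describes the test that will be run.

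**Working it through.** **Inputs.** From Sample Size Determination: incidence 0.50 and 0.10, alpha 0.05, power 80%, 23 per group. From Study Design: 30 per arm. Assumed: two-sided tests, no covariates and, unless stated, equal exposure.

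**1. Reproduce the 23.** Let a and b be the numbers of affected infants, independent binomials (n, 0.50) and (n, 0.10). Summing their joint probabilities over all tables where Fisher's two-sided p ≤ 0.05 gives power 78.6% at n = 22 and 81.1% at n = 23. So 23 is what Fisher's exact test needs. (The pooled normal formula gives 20, and its continuity-corrected form 25.) The stated figure belongs to a yes/no comparison.

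**2. Standard error of the log ratio at n = 23.**
- Poisson, model-based: √(1/(n·pA) + 1/(n·pB)) = √(1/11.5 + 1/2.3) = 0.722
- Correct for 0/1 data: √((1−pA)/(n·pA) + (1−pB)/(n·pB)) = √(0.5/11.5 + 0.9/2.3) = 0.659
- Ratio: 0.722/0.659 = 1.095, or 9.5% too large

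Under no difference the ratio is 1/√(1−p): 1.20 at p = 0.3 and 1.41 at p = 0.5.

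**3. Size and power by the same enumeration.** Wald rejects when |ln(a/b)|/√(1/a + 1/b) > 1.96, and an arm with no events counts as non-significant. Likelihood ratio rejects when 2[a·ln(a/m) + b·ln(b/m)] > 3.84, with m = (a+b)/2.

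| | Poisson Wald | Poisson likelihood ratio | Fisher |
|---|---|---|---|
| Size, p = 0.5, n = 23 / 30 | 0.5% / 0.5% | 0.7% / 0.7% | 2.6% / 2.7% |
| Size, p = 0.3, n = 23 / 30 | 1.1% / 1.5% | 2.8% / 2.3% | 2.5% / 2.6% |
| Size, p = 0.1, n = 23 / 30 | 0.1% / 0.2% | 8.3% / 7.4% | 1.6% / 0.9% |
| Power, n = 20 | 49.4% | 77.0% | 74.2% |
| Power, n = 23 | 63.1% | 82.1% | 81.1% |
| Power, n = 30 | 83.2% | 90.7% | 91.4% |

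Poisson Wald reaches 80% at 29 per group (78.9% at 28, 81.1% at 29).

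**4. Unequal exposure (assumed scenarios, 3,000 simulated trials).** The hazard is constant and set to give 50% and 10% by week 12; whole time on TPN is the offset.
- One third of infants stop TPN between weeks 3 and 12: Wald 51% and likelihood ratio 75% at 23 per group; 76% and 88% at 30.
- All infants stop uniformly between weeks 3 and 12: 25% and 64% at 23; 50% and 78% at 30. Part of this fall comes from fewer events in a shorter follow-up, not from the model.

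**The case against.** Several points on the other side stand.

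- **Enrolment is 30 per arm, not 23.** A reader might infer that the trial is underpowered for PNAC. The documents do not support that: at 30 per arm with equal exposure both Poisson tests exceed 80%. At 23 the shortfall depends on a Wald test, which the plan does not name.
- **Part of the Wald loss is a small-sample effect.** At 10% incidence and n = 23 an arm has no events with probability 0.9^23 = 8.9%. Wald logistic regression (77%) and Poisson with robust variance and a Wald test (74%) also miss 80% at 23.
- **The Poisson test is not conservative everywhere.** The likelihood-ratio version is anti-conservative at 10% incidence.
- **The plan does not say that PNAC happens once per infant.** That is a strong inference from the threshold definition and the percentage-based sample size. But item 3 counts occurrences and item 1 refers to a first one. EFAD can recur, since profiles are repeated every two weeks until it resolves. If repeats are meant to count, however, the count is undefined and the 23 does not apply to it.
- **The offset wording is ambiguous.** It is the septic-episode analysis, not item 3, that uses the total time on PN. Length of time on PN is a recognised PNAC risk factor, which gives the offset a rationale.
- **Other binary methods appear in the plan.** Fisher's exact test and logistic regression are listed in general terms under Planned Statistical Analysis, but item 3 assigns this outcome to Poisson. The sentence "A logistic regression with Generalized Estimating Equations (GEE) approach will be used to compare the binary outcomes between groups" closes the neurodevelopmental item and does not cover PNAC.

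**Conclusion.** The point holds as a mismatch between the sample size and the analysis, together with a wrong variance. With PNAC counted yes/no per infant, model-based Poisson intervals are too wide: the standard error is 9.5% too large at the planning values, and 20% to 41% too large under no difference at 30% to 50% incidence. Neither Poisson test holds its nominal level across the plausible range, and the negative binomial fallback cannot correct this.

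The power loss is narrower than it may look. It applies to Wald at 23 per group (63%), to fewer evaluable infants (at 20 per arm Fisher's test also falls short, at 74%), or to shorter or unequal exposure. At the planned 30 per arm with equal exposure, power is 83% or 91%.

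The size and power figures assume two-sided tests and no covariates, so they do not describe the fully adjusted model in item 3. Any dilution through the offset depends on how much longer cholestatic infants stay on TPN, which the documents do not give. This is a secondary outcome. The change should be made because the intervals are wrong as written and the correction is cheap.

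**What to change.** In Secondary Outcome Measures, item 3:

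1. Define PNAC and severe PNAC incidence as yes/no per infant. Name Fisher's exact test, which matches the 23 per group, as the stated comparison, without the TPN offset. Report risk difference and risk ratio with 95% confidence intervals.
2. Use logistic regression with likelihood-ratio tests for any adjusted analysis. Treat it as supportive, because its unadjusted form also has size 8.3% at 10% incidence and 23 per group.
3. Leave time at risk to the Cox analysis of first occurrence already planned in item 1.
4. Analyse any occurrence of EFAD in the same yes/no way. Use a count model only if repeat episodes are explicitly defined.
5. Keep Poisson or negative binomial regression with the offset for septic episodes, which are repeatable.
6. In Sample Size Determination, name the test and its sidedness behind the 23.

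The cost is SAP wording only: no new data and no more infants.

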The standard dosing for IVFE in neonates is 3 g/kg/day. The development of PNAC while on this dosing regimen often leads practitioners to reduce the IVFE dose in an attempt to reverse or keep the liver dysfunction and fibrosis from progressing. The data supporting IVFE reduction (IFER) focus on the efficacy of this modification after the first signs of PNAC have developed rather than as a preventative approach. The benefit of IFER was first described in the adult literature in 1982 but it was not until 2000 that a similar approach was reported in a pediatric population with severe cholestasis.^{17,18} In this report by Colomb et al the IVFE component of PN was acutely terminated once cholestasis developed (defined as a plasma bilirubin ≥ 30 $\mu\text{mol/L}$). Patients were subsequently noted to have a marked decline in bilirubin levels.¹⁸ A prospective study by Cober and Teitelbaum supported this concept of IFER for the prevention of PNAC progression.^{19,20} In this single-center study, patients who developed PNAC (defined as a direct bilirubin >2.5 mg/dL) on standard soybean-based IVFE at a dose of 3 g/kg/day were switched to a restricted regimen of IVFE at a dose of 1 g/kg/day twice a week. These infants were then compared to a well-matched historical controls who were maintained on standard IVFE dosing regardless of bilirubin level. Thirty-one patients were included in the study group and were noted to have a significant decline in their serum direct bilirubin levels over time when compared to the control group. Specifically, the IFER group was found to have a downward trend in bilirubin whereas the standard cohort was found to have increased bilirubin levels across study weeks (estimated slope -0.73 mg/dL/week compared to 0.29 mg/dL/week; $p=0.0017$). In addition, the number of patients achieving resolution of PNAC was significantly greater in the IFER group compared to the control group ($n=13$ vs. $n=3$; $p=0.013$). It is important to note that eight patients in the IFER group developed mild, reversible essential fatty acid deficiency (EFAD) which was

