IVFE reduction (IFER) during the administration of neonatal parenteral nutrition will lead to a significant decrease in the rate of rise of direct bilirubin (mg/dL/week) when compared to standard therapy.

Secondary Hypotheses

1. The time to development of PNAC, when present, will be longer with IFER when compared to standard IVFE therapy.
2. IFER will not be associated with a significant increase in failure to thrive (as assessed by growth parameters) or the development of essential fatty acid deficiency (EFAD) when compared to standard IVFE therapy.
3. Neurodevelopmental outcomes (NDOs), when assessed at 12 and 24 months of corrected gestational age, will be similar for those treated with IFER and standard IVFE therapy.

Specific Aims

1. To determine whether neonates and infants receiving PN with IFER (1 g/kg/day) will have lower rates of rise of direct bilirubin compared to those receiving standard IVFE therapy (3 g/kg/day)
2. To compare the time to development of PNAC in neonates and infants receiving PN with IFER (1 g/kg/day) compared to those receiving PN with standard IVFE administration (3 g/kg/day)
3. To determine if IFER results in normal growth and essential fatty acid (EFA) parameters by measuring weight, length, head circumference (weekly) and EFA profiles (every 2 weeks in the IFER group) during the treatment period.
4. To compare NDOs at 12 and 24 months of corrected gestational (± 2 weeks) age of those treated with IFER with those treated with standard IVFE doses using a combination of neurodevelopmental screening tools (e.g. Bayley Scales of Infant Development, MacArthur Communicative Development Inventory, etc.) aimed at capturing several developmental domains such as motor, cognition, speech and language, sensory, and behavior.

Study Definitions

Subjects will be considered “on treatment” from the time of randomization until 7 days after PN has been discontinued, but not to exceed a total of 84 days. Subjects will be considered “on study” until they complete their neurodevelopmental testing at 24 months corrected gestational age (± 2 weeks).

Study Design

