 - iii. Brief Infant Toddler Social Emotional Assessment (BITSEA)
 - iv. Gross Motor Function Classification System (GMFCS)
 - v. Behavioral Assessment System for Children-Second Edition (BASC2)

Study Arms:

[figure not shown]
Study Arm 1 (Standard IVFE dosing): Subjects in the standard IVFE dosing arm (3 g/kg/day) will be on treatment for a total of 12 weeks or until the subject has been off of parenteral nutrition for >7 days, or if they are discharged from the hospital, whichever comes first.

Study Arm 2 (IFER dosing): Subjects in the IFER dosing arm (1 g/kg/day) will be on treatment for a total of 12 weeks or until the subject has been off parenteral nutrition for >7 days, or if they are discharged from the hospital, whichever comes first.

All subjects will be maintained at their assigned dosing regimen for the duration of the treatment period (12 weeks) or until they are transitioned off of PN for >7 days, are discharged or until the direct bilirubin is ≥ 2.5 mg/dL for 2 consecutive weeks, whichever occurs first. Data will be collected for the duration of the study for those subjects who remain on parenteral nutrition for the full 12 weeks. For those who transition off of PN prior to the end of the 12 week period, data will be collected for 7 days after termination of PN if the subject remains in the hospital. The clinical course of these subjects who wean off PN prior to 12 weeks will continue to be monitored according to standards of practice. If serum direct bilirubin reaches a level of ≥ 2.5 mg/dL for 2 consecutive weeks during the course of the treatment, subjects will be transitioned to an IVFE dose of 1 g/kg/day three days per week. Those who remain cholestatic at the termination of their treatment period will be evaluated on a monthly basis for the persistence or resolution of cholestasis. This will be done by obtaining monthly liver function tests and bilirubin fractions for 6 months.

Overview of Study Design:

Study Design

Inclusion Criteria

Study subjects will be neonates and infants who are ≥ 28 weeks corrected gestational age at the time of enrollment who are parenteral nutrition naïve (<72 hours of PN exposure prior to randomization) and whose direct bilirubin has never been >2 mg/dL with at least one of the following diagnoses:

1. Meconium ileus and peritonitis
2. Gastroschisis
3. Omphalocele >4 cm in diameter or with liver herniated outside of the abdominal cavity

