1. If TG are <250 mg/dL: restart IVFE at 50% of previous dose
2. If TG are ≥250 mg/dL: continue to hold IVFE infusion and repeat TG level every 48 hours until <250 mg/dL. If IVFE is held for ≥7 days with continued TG levels ≥250 mg/dL, restart IVFE at 0.5 g/kg/day

Essential Fatty Acid Deficiency (EFAD)

The detection of EFAD will be assisted by a biochemist and expert in the area of lipid biology.

The IVFE dose will be adjusted if subjects develop EFAD. EFAD will be defined by the development of any of the following:

1. Clinical evidence of EFAD deficiency (i.e. scaly skin)^{31,32}
2. Triene:tetraene ratio of >0.20
3. Arachidonic acid (ARA), (EPA) and/or docosahexaenoic acid (DHA) levels below normal as defined by Mayo Laboratory reference ranges

In the presence of EFAD, the IVFE dose will be increased in 0.5 g/kg/day increments based on biweekly essential fatty acid profiles until resolved.

Cycled Parenteral Nutrition

Study subjects will not receive cycled parenteral nutrition (i.e. parenteral nutrition administered over less than 24 hours per day) during the study period, as cycled PN has been shown to decrease the development of PNAC and may represent a confounder.^{33,34}

Adjustment of Parenteral Nutrition if Inadequate Weight Gain Occurs

(Lipid Restricted Group Only)

Subjects with inadequate weight gain that cannot be attributed to other physiologic causes (e.g. low urine sodium, low hematocrit, insufficient respiratory support) will be managed according to the protocol described below.

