3. Weight, gestational age at the time of enrollment/randomization, and weekly thereafter
4. Inclusion diagnosis
5. Number of septic episodes according to standard definitions³⁸
6. Use of choleric medications
 - a. Ursodiol
 - b. Cholecystokinin
 - c. Phenobarbital
7. Nutritional data
 - a. Parenteral nutrition data
 - i. IVFE dose
 - ii. Dextrose infusion rate
 - iii. Total calories and % calories obtained via PN
 - b. Enteral nutrition data
 - i. Total calories and % calories being obtained via enteral route
 - ii. % calories obtained via breast milk
8. Growth parameters (whenever possible, obtain all growth measurements on the same day of the week)
 - i. Weight (with z-score) weekly (every 7 days ± 2 days)
 - ii. Height (with z-score) weekly (every 7 days ± 2 days)
 - iii. Head circumference (with z-score) weekly (every 7 days ± 2 days)
9. Additional safety data to be obtained from human subjects is summarized below, indicating any key differences in frequency of monitoring between the two groups:

Laboratory Parameter	Frequency (+24 hours)*
Fractionated bilirubin panel (includes total, indirect, and direct bilirubin)	One time weekly (Monday)
Serum bile acids (total)	One time monthly (every 4 th Monday on treatment)

Point of care or serum glucose measures	- Daily for the first 5 days of PN, then twice weekly (Monday, Thursday) - Confirmatory test if serum glucose is >150 mg/dL on electrolyte panel
Serum Triglycerides	One time weekly (Monday)
Essential Fatty Acid Profile	IFER Group: Every 2 weeks (Thursday) Standard Group: At the time of restriction of IVFE to 1 g/kg/day three days per week, then every 2 weeks (Thursday)
Comprehensive metabolic panel	Twice weekly (Monday, Thursday)
Magnesium level	Twice weekly (Monday, Thursday)
Phosphorus level	Twice weekly (Monday, Thursday)
Complete blood count	One time weekly (Monday)

* Lab draw volumes will be below each institution's daily limits

Definition of Sepsis

Sepsis will be defined in a standard manner using the following criteria (**Table 2**):³⁸

The presence of at least two of the following four criteria ***in the presence of or as a result of suspected or proven infection***:

1. Core temperature of >38.5C or <36C

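### Fatty acid profiles are scheduled throughout treatment only in the IFER arm, yet the EFAD rate model uses time on TPN as its offset, so it cannot serve as the between-arm test of laboratory-defined EFAD under secondary hypothesis 2

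*Combined protocol and SAP*

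**What the plan says.** **Hypothesis.** Secondary hypothesis 2 is comparative: IFER will not bring a significant increase in failure to thrive "or the development of essential fatty acid deficiency (EFAD) when compared to standard IVFE therapy".

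**Definition.** Under Essential Fatty Acid Deficiency (EFAD), any one of three findings is enough: clinical signs (scaly skin), a triene:tetraene ratio above 0.20, or "Arachidonic acid (ARA), (EPA) and/or docosahexaenoic acid (DHA) levels below normal as defined by Mayo Laboratory reference ranges". The second and third need a fatty acid profile. A positive finding also changes treatment: "In the presence of EFAD, the IVFE dose will be increased in 0.5 g/kg/day increments".

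**Testing schedule.** The laboratory table under Data Collection schedules the profile every 2 weeks for IFER. For the comparator it reads "Standard Group: At the time of restriction of IVFE to 1 g/kg/day three days per week, then every 2 weeks (Thursday". Specific Aim 3 also names the 2-weekly profile for the IFER group only.

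**Trigger for standard-arm testing.** Under Study Arms, once direct bilirubin has been at least 2.5 mg/dL for 2 consecutive weeks, "subjects will be transitioned to an IVFE dose of 1 g/kg/day three days per week".

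**Analysis.** Item 3 of Secondary Outcome Measures compares EFAD counts between arms by Poisson or negative binomial regression. It adds "We will also include the time on TPN as an offset", and then: "These regression models will be adjusted for the covariates such as development of sepsis, average IVFE dose, and percentage of enteral feeds". Potential Confounding Variables also names duration of IVFE/IFER as a covariate.

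**The concern.** A rate model is fair between arms only if its denominator is time during which the event could have been recorded. Here the denominator is time on TPN, while laboratory EFAD can be recorded only where a profile is drawn. An IFER infant is tested throughout. A standard-arm infant who never meets the bilirubin trigger has no scheduled profile, but all of that infant's TPN time enters as event-free for two of the three criteria.

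The standard-arm infants who are tested are also not representative of their arm. All are cholestatic, and every profile after the first follows a cut to 3 × 1 = 3 g/kg per week. IFER infants receive 7 × 1 = 7 g/kg per week, and the assigned standard dose is 7 × 3 = 21.

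EFAD is a central safety question for lipid restriction. A between-arm rate driven largely by who was tested could wrongly count against IFER. After adjustment it could also wrongly reassure.

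**Working it through.** The documents give no EFAD rate, margin or power, so there is no planned figure to reproduce. The check has four steps.

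**1. Unadjusted bias.** Let λ be the true rate of laboratory-detectable EFAD, equal in both arms, T the TPN time per arm, and s the share of standard-arm TPN time under testing. Expected counts are λT in IFER and λsT in the standard arm. With offset T in both, the rate ratio is λT / (λsT) = 1/s.

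**2. What s might be.** The documents do not give it. If a proportion p of the standard arm is restricted at week w of 12, then s = p × (12 − w)/12. The values of p and w below are assumptions:

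| p | w | s | 1/s |
|---|---|---|---|
| 0.50 | 4 | 0.33 | 3 |
| 0.50 | 8 | 0.17 | 6 |
| 0.25 | 4 | 0.17 | 6 |
| 0.25 | 8 | 0.083 | 12 |
| 0.10 | 4 | 0.067 | 15 |

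The 50% cholestasis incidence in Sample Size Determination is for the PNAC threshold of 2 mg/dL. The restriction threshold is higher, so p = 0.50 is a generous value.

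The same section allows a more specific estimate. Its standard-arm means are 0.55, 1, 1.5 and 2 mg/dL at weeks 0, 4, 8 and 12, with SD 1 and correlations 0.5, 0.354 and 0.25 at lags of 4, 8 and 12 weeks. I took normal values and weekly measurement, interpolated the means linearly, and filled in the weekly correlations three ways (linear, log-linear, and 0.5^(0.5 + lag/8), which passes through all three stated values). I then found the first pair of consecutive weekly values of at least 2.5 mg/dL in 400,000 simulated infants, all on PN for the full 12 weeks.

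- Restricted by week 4: 4–5%. By week 8: 12–16%. By week 12: 29–33%.
- Mean weeks remaining after restriction: 3.5–3.9.
- s = 0.287 × 3.53/12 = 0.084 to 0.333 × 3.90/12 = 0.108.
- 1/s = 12 to 9.

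On these assumptions, about 20 or 21 of 30 standard-arm infants would never have a scheduled profile (30 × 0.667 = 20; 30 × 0.713 = 21). The normal model is crude, since it allows negative bilirubin values.

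The 1/s rule is also approximate. If each infant counts once and repeat profiles are correlated, the inflation is smaller. Example under assumptions not in the documents: no infant is truly deficient; the chance of at least one low acid is 0.164 with six profiles and 0.113 with three; 20 IFER infants have six profiles and 10 have three; 25% of standard infants are tested with three each. Expected positives are 20 × 0.164 + 10 × 0.113 = 4.41 against 30 × 0.25 × 0.113 = 0.85, a ratio of 5.2. Tested time is 45 of 300 infant-weeks, so s = 0.15 and 1/s = 6.7.

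**3. Chance of a significant unadjusted IFER excess when true rates are equal** (exact conditional Poisson comparison, two-sided 0.05, equal TPN time):

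| True events per arm | s = 1 | s = 0.17 | s = 0.07 |
|---|---|---|---|
| 3 | 0.6% | 5.4% | 7.0% |
| 6 | 1.2% | 31% | 44% |
| 12 | 1.5% | 72% | 90% |

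**4. Whether the planned covariates repair it.** None measures testing directly. Average IVFE dose largely encodes arm (3 against 1 g/kg/day), falls in exactly those standard infants who become tested, and is raised by EFAD itself, so part of it is a consequence of the outcome. Duration of IFER, if it means time on reduced lipid, would track tested time in the standard arm, but the plan does not define it that way. Sepsis and enteral feeding say nothing about who was tested. The size and sign of the remaining bias depend on quantities that the documents do not give.

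**The case against.** **The planned model is adjusted, so the unadjusted inflation is not its result.** This stands. The ratios above describe the unadjusted rate, not the full planned model. A reader might infer that the planned analysis must show excess EFAD under IFER. The documents do not support that, because the adjusted estimate could fall on either side of 1.

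**EFAD can be seen without a profile.** Also correct. Scaly skin is sufficient on its own and can be recorded in either arm, and EFAD is a listed expected adverse event. It would be too strong to say that untested time counts as free of all EFAD. The statement holds for the two laboratory criteria.

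**Aim 3 is already about IFER.** It asks whether IFER gives normal essential fatty acid parameters, and the laboratory table announces different monitoring by group. That supports an IFER-arm description as the main result. It does not support the between-arm regression or the comparative wording of hypothesis 2.

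**EFAD is expected to be very rare, and other secondary outcomes are for trends only.** With few events a false significant excess is unlikely (the 3-event row above), and this limits the priority. But the expectation is not secure. The background reports that "eight patients in the IFER group developed mild, reversible essential fatty acid deficiency (EFAD) which was" defined by a lower cut-off, in 8 of 31 infants (26%) on a sparser regimen, and this trial's definition adds low individual acids. A trend produced by testing frequency would still mislead.

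**Equal testing would be the better repair.** For a randomized laboratory comparison, it would. It costs extra neonatal blood draws, up to six profiles per infant over 12 weeks.

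**Conclusion.** The concern holds as a minor to moderate point on a secondary safety outcome. Unequal testing, a TPN-time offset and a comparative hypothesis are all in the text, and together they bias the unadjusted between-arm rate of laboratory-defined EFAD against IFER when true rates are equal. The inflation is roughly 1/s. Under the protocol's bilirubin assumptions (normal values, weekly, full 12 weeks on PN) s is about 10%, which implies an inflation of about 9 to 12, or less if each infant counts once. Those figures rest on assumptions. The existence and direction of the unadjusted bias do not, provided true rates are equal. After the planned adjustment, neither size nor direction can be determined from the documents.

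A reader might also infer that the trial's efficacy result is affected. Nothing here bears on the primary outcome: bilirubin is scheduled weekly without distinction by arm.

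**What to change.** Change the SAP wording as follows.

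1. State that the TPN-time-offset model of laboratory-defined EFAD, with or without covariates, will not be used as the between-arm test of secondary hypothesis 2.
2. Report EFAD by arm and by criterion (ratio above 0.20, low individual acid, scaly skin), with infants tested, profiles drawn and positive profiles.
3. Make IFER-arm incidence with an exact 95% confidence interval the main EFAD result, in line with Aim 3. With 0 of 30 the upper limit is 1 − 0.025^(1/30) = 11.6%; with 3 of 30 the interval is 2.1% to 26.5%.
4. Compare arms only on clinical EFAD, which can be observed in both.
5. Label any per-profile rate in the standard arm as descriptive and non-randomized, because it comes from cholestatic infants, mostly after the cut to 3 g/kg per week.

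An analysis restricted to the ratio criterion would not help with unequal testing, because it needs the same profile.

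**Cost.** No extra draws and no change to care, the EFAD definition or the dose rule. The price is that no randomized between-arm test of laboratory EFAD remains, and the IFER interval is wide. Clinical EFAD is likely to be sparse and is judged by an unblinded care team. If the sponsor wants a randomized laboratory comparison, both arms need the same 2-weekly profiles.
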